#### 7.11.5. Reserve Blood Samples

Additional blood samples from subjects may be collected starting at Visit 2 and at up to four (4) additional study visits for investigational assessment of biomarkers that could be associated with the cellular viability and durability of the implanted VC-02 product. The number of biomarkers assessed will be limited by the amount of sample available, but will not include any genetic testing. If the additional blood samples are collected, as much as 5 mL of blood could be collected at each time point. Results of these tests may not be reported to the site during the course of the study. Additional details may be provided in a separate laboratory manual.

#### 7.11.6. Blood Volumes

Total blood collection volumes from scheduled visits requiring lab assessments are not planned to be greater than 700 mL over the course of the trial. Of the 18 clinic visits, there are five (5) visits where blood volumes are estimated to be up to approximately 80 mL: Visit 2 (Week -4), Visit 11 (Week 26), and Visit 13 (Week 52), and Visit 17 (Week 104). At other visits, the blood volume required ranges from 0 mL to 60 mL.

If all allowed reserve blood samples (Section 7.11.5) are collected, this would result in up to an additional 25 mL of blood collected during the trial.

Additionally, it is expected that up to approximately 15 mL of blood may be collected each time the site tests the immunosuppression drug concentrations and the associated safety tests.

For all subjects, blood collections are not planned to occur more frequently than once per week unless there is a need for an Unplanned Visit.

## 7.12. Clarke Survey

The Clarke Hypoglycemia Unawareness Survey (Appendix 1) is a validated scoring system used to measure the degree of awareness a subject with T1DM has to symptoms associated with hypoglycemia (Gold, Macleod, & Frier, 1994). It will be administered at Screening Visit 1 to determine if the inclusion criterion (score  $\geq 4$ ) is met. Subjects will then complete the Clarke Survey at the following additional time points: Visit 9 (Week 16), Visit 11 (Week 26), Visit 12 (Week 39), Visit 13 (Week 52), Visit 15 (Week 78), and Visit 17 (Week 104).

## 8. SAFETY REPORTING

The Investigator is required to report all directly-observed AEs, all spontaneously reported AEs, and any pregnancies experienced by study subjects. In addition, each study subject will be questioned about AEs and pregnancies (if applicable) at each clinic visit.

## 8.1. Adverse Events

An adverse event (AE) is any untoward medical occurrence in a clinical investigation subject administered a product or medical device. Adverse events need not necessarily have a causal relationship with the treatment or usage.

Examples of AEs include, but are not limited to:

- Abnormal test findings;
- Clinically significant symptoms and signs (changes from baseline status);
- Clinically significant changes in physical examination findings;
- Hypersensitivity;
- Sensitization to the
- Progression/worsening of underlying disease (includes worsening diabetes, as assessed by the Investigator)

All observed or volunteered AEs regardless of suspected causal relationship to the investigational product will be reported as described in the following sections.

For all AEs, the Investigator must pursue and obtain information adequate both to determine the outcome of the AE and to assess whether it meets the criteria for classification as a serious adverse event (SAE) requiring immediate notification to the Sponsor and the Ethics Committee. For all AEs, sufficient information should be obtained by the Investigator to determine the causality of the AE. The Investigator is required to assess causality. Follow-up by the Investigator may be required until the event or its sequelae resolve or stabilize at a level acceptable to the Investigator, and the Sponsor concurs with that assessment.

As part of ongoing safety reviews conducted by the Sponsor, any non-serious AE that is determined by the Sponsor to be serious will be reported by the Sponsor as a SAE. To assist in the determination of case seriousness, further information may be requested from the Investigator to provide clarity and understanding of the event in the context of the clinical trial.

As required on the AE CRFs, the Investigator will use the National Cancer Institute Common Terminology Criteria for Adverse Event (NCI-CTCAE) guidelines to describe the maximum intensity of the AE. For purposes of consistency, these intensity grades are defined as follows:

MILD	Asymptomatic, or mild symptoms, clinical or diagnostic observations noted; intervention not indicated.
MODERATE	Local or noninvasive intervention indicated.
SEVERE	Medically significant but not immediately life threatening, hospitalization or prolonged hospitalization.
LIFE-THREATENING	Life-threatening consequences, urgent intervention indicated.
DEATH	Death related to AE.

Note the distinction between the severity and the seriousness of an AE. A severe event is not necessarily an SAE. For example, a headache may be severe (medically significant) but would not be classified as serious unless it met one of the criteria for SAEs (See Section 8.2).

In addition, if the Investigator determines an SAE is associated with study procedures, the Investigator must record this causal relationship in the source documents and CRF, as appropriate, and report such an assessment in accordance with the SAE reporting requirements, if applicable.

It should be noted that the form for collection of SAE information may not be the same as the AE CRF. Where the same data are collected, the forms must be completed in a consistent manner. AEs should be reported using concise medical terminology.

## 8.1.1. Causality Assessment of Adverse Events

The Investigator's assessment of causality must be provided for all AEs (serious and non-serious). In relation to implantation with VC-02, there are three (3) main components to assessing causality. The Investigator's causality assessment must include a determination of whether there exists a reasonable possibility that:

- The investigational product (VC-02) itself caused or contributed to the AE.
- The surgical procedure (implantation or explanation) caused or contributed to the AE.
- The immunosuppression drug regimen caused or contributed to the AE.

In evaluating the causal relationship of an AE to VC-02, the surgical procedures, and the immunosuppression regimen, it is possible for the Investigator to determine causality as being associated to one or more of these factors. Conversely, the Investigator can determine that none of these relate to the AE.

If the Investigator's final determination of causality is unknown, and the Investigator does not know if the investigational product, surgical procedure, or immunosuppression drugs caused the event, then the event will be classified as "related to investigational product" for reporting purposes. If the Investigator's causality assessment is "unknown but not related to investigational product", this should be clearly documented on study records.

Relationship of an AE to VC-02, the surgical procedures, and the immunosuppression drugs will be assessed as follows:

Not Related (Unrelated or Unlikely Related): A clinical event including laboratory test abnormalities without a temporal relationship to the investigational product exposure, the surgical

procedures, or the immunosuppression drugs, which makes a causal relationship improbable, and/or in which other drugs, chemicals, or underlying disease provides plausible explanations.

**Possibly Related:** A clinical event, including laboratory test abnormality, with a reasonable time sequence to exposure of the investigational product, the surgical procedures, or the immunosuppression drugs, but which could also be explained by concurrent disease or other drugs or chemicals.

**Definitely Related:** A clinical event, including laboratory test, occurring in a plausible time relationship to the investigational product exposure, surgical procedures, or the immunosuppression drugs, and which cannot be explained by concurrent disease or other drugs or chemicals.

### 8.1.2. Expected Adverse Events

Refer to Section 1.4.1.

### 8.1.3. Determination of Abnormal Laboratory Test Values or Abnormal Clinical Findings as Adverse Event

The criteria for determining whether an abnormal, objective test finding should be reported as an AE are as follows:

- Test result is associated with accompanying symptoms, and/or
- Test result is not associated with a known, pre-existing condition or part of the subject's medical history, and/or
- Test result requires additional diagnostic testing or medical/surgical intervention, and/or
- Test result leads to discontinuation from the study, significant additional concomitant drug treatment, or other therapy, and/or
- Test result is considered to be an AE by the Investigator or sponsor.

Merely repeating an abnormal test, in the absence of any of the above conditions, does not constitute an AE. An abnormal test result determined to be an error does not require reporting as an AE.

Evidence of product sensitization (the presence of donor anti-HLA antibodies absent prior to implant) is not in itself considered an AE. The above criteria should also be utilized to determine if the sensitization qualifies as an AE.

## 8.1.4. Adverse Events of Special Interest (AESI)

Certain AEs may require additional investigation to ensure appropriate information and data are captured to appropriately evaluate the clinical development of VC-02. These are considered adverse events of special interest (AESI) and may include but are not limited to:

- AEs leading to the unexpected or premature explantation of VC-02-300 or sentinel units are considered AESI.
- AEs that result in early withdrawal from the study.

• Severe hypoglycemic events occurring after VC-02 implantation possibly or definitely related to VC-02.

If an AESI occurs, the Sponsor may request that additional data be collected for these events.

### 8.1.5. Period of Observation and Reporting

All AEs with a start date occurring between Visit 2 (Week -4) and through the last subject visit must be recorded on the CRF. During the study, sites should query subjects on the status of any ongoing AEs at subsequent clinic visits. Depending on the reported event, the Investigator may need to follow-up on the status of AEs with the study subject between visits (e.g., phone, text, or email). At the conclusion of the trial, any ongoing AEs will be followed until at least 28 days after the final explantation procedure to determine the final reported outcome of the event.

For SAEs, including pregnancy reports, the active reporting period to the Sponsor begins from the time the subject provides informed consent through and including 28 days after the final explantation of all of the investigational product units.

SAEs occurring after the period of observation has ended should be reported to the Sponsor if the Investigator becomes aware of an event. At a minimum, all SAEs the Investigator assesses as possibly related to the investigational product are to be reported to the Sponsor.

The reporting period for AEs and SAEs may overlap with the timing of the subject's participation in the mandatory, long-term follow-up study. Further details on how to report ongoing AEs spanning the period between the VC02-101 protocol and follow-up study will be outlined in the separate follow-up protocol.

All AE reporting, including SAEs and SUSARs, will be carried out in accordance with applicable regulations.

## 8.2. Serious Adverse Events (SAE)

An SAE is any untoward medical occurrence meeting at least one of the following criteria:

- Results in death;
- Is life-threatening (immediate risk of death);
- Requires in-patient hospitalization or prolongation of existing hospitalization;
- Results in persistent or significant disability/incapacity (substantial disruption of the ability to conduct normal life functions);
- Results in congenital anomaly/birth defect;
- Constitutes an Important Medical Event in the opinion of the Investigator and/or Sponsor.

Medical and scientific judgment is exercised in determining whether an event is an important medical event. An important medical event may not be immediately life threatening and/or result in death or hospitalization. However, if it is determined the event may jeopardize the subject or may require intervention to prevent one of the other SAE criteria, the important medical event should be reported as serious.

ViaCyte Inc., Confidential

Based on the definition above, severe hypoglycemic events (SHE) may or may not be reported as SAEs and will be classified at the Investigator's discretion. In all instances, SHEs are to be recorded on the hypoglycemic event (HE) CRF.

AEs resulting in hospitalization or prolongation of a hospitalization are considered serious. Any formal admission (even if less than 24 hours) to a healthcare facility meets these criteria. Admission also includes transfer within the hospital to an acute or intensive care unit (e.g., from the psychiatric wing to a medical floor, medical floor to a coronary care unit, neurological floor to a tuberculosis unit).

Hospitalization does not include the following:

- Rehabilitation facilities;
- Hospice facilities;
- Respite care (e.g., caregiver relief);
- Skilled nursing facilities;
- Nursing homes;
- Emergency room visits;
- Outpatient surgical procedures.

Hospitalization or prolongation of hospitalization in the absence of a precipitating, clinical AE is not in itself an SAE. Examples include:

- Admission for treatment of a pre-existing condition not associated with the development of a new AE or with a worsening of the preexisting condition (e.g., for work-up of persistent pre-treatment lab abnormality);
- Social admission (e.g., subject has no place to sleep);
- Administrative admission (e.g., for yearly physical exam);
- Protocol-specified admission during a study (e.g., for a procedure required by the study protocol);
- Optional admission not associated with a precipitating clinical AE (e.g., for elective cosmetic surgery);
- Hospitalization for observation without a medical AE;
- Pre-planned treatments or surgical procedures should be noted in the baseline medical history assessment and documentation for an individual subject.

Diagnostic and therapeutic non-invasive and invasive procedures, such as surgery, should not be reported as AEs. However, the medical condition for which the procedure was performed should be reported if it meets the definition of an AE. For example, an acute appendicitis that begins during the AE reporting period should be reported as the AE, and the resulting appendectomy should be recorded as treatment of the AE.

Protocol #VC02-101

## 8.2.1. Suspected, Unexpected Serious Adverse Reactions (SUSAR)

A SUSAR is a serious adverse reaction which is thought to be causally related to the investigational product, surgical procedure, and/or immunosuppression regimen and which is unexpected to occur. Reporting of SUSARs to the Sponsor, all participating Investigators, the Ethics Committee, and to the Regulatory Authorities is mandatory in accordance with applicable regulations.

Because of the limited shelf-life of the investigational product, the results of the 14-day sterility testing of VC-02 are not available until after implantation occurs. In the unexpected event of positive culture results from this test, the Sponsor will notify the Investigator, who will then notify the subject. The Sponsor will initiate further testing of the positive sample to identify the microorganism and conduct a root-cause analysis. The Investigator and Sponsor will evaluate any additional actions required to appropriately monitor the subject based on the results of the sample. If the medical condition of the patient is impacted as a consequence of the microorganism causing the positive sterility results, the event should be reported as a SUSAR.

## 8.2.2. SAE Reporting Procedures

If an SAE occurs, the Sponsor must be notified within 24 hours of the Investigator becoming aware of the occurrence of the event. In particular, if the SAE is fatal or life-threatening, notification to the Sponsor must be made immediately, irrespective of the extent of available AE information. This timeframe also applies to additional, new information (follow-up) on previously reported SAE reports as well as to the initial and follow-up reporting on cases of exposure during pregnancy and exposure via breastfeeding.

In the rare event the Investigator does not become aware of the occurrence of an SAE immediately (e.g., a study subject initially seeks treatment elsewhere), the Investigator is to report the event within 24 hours after learning of it and document the date and time of awareness of the AE.

For all SAEs, the Investigator is obligated to pursue and provide information to the Sponsor in accordance with the timeframes for reporting specified above. In addition, an Investigator may be requested by the Sponsor to obtain specific, additional, follow-up information in an expedited fashion. The information collected for SAEs is more detailed than that captured on the AE CRF. In general, this will include a description of the SAE in sufficient detail to allow for a complete medical assessment of the case and independent determination of possible causality. Information on other possible causes of the event, such as concomitant medications and illnesses must be provided. In the event of a subject death, a summary of available autopsy findings must be submitted as soon as possible to the Sponsor.

# 8.3. **Reporting of Pregnancy**

For investigational products, an exposure during pregnancy (referred to as Exposure in Utero [EIU]) occurs if an enrolled female subject becomes, or is found to be, pregnant while in the study. In addition, if a male subject reports that his partner has become pregnant while he has had VC-02 units implanted, this will also be captured as an EIU. Pregnancy itself is not an AE. However, adverse consequences of pregnancy should be reported as an AE or SAE as applicable.

If the subject or the subject's partner becomes or is found to be pregnant during the study, the Investigator must submit this information to the Sponsor on an EIU Form. This must be done within 24 hours of awareness of the event. The information submitted should include the anticipated date of delivery (see below for information related to termination of pregnancy). All confirmed EIU cases and follow-up information will be recorded in a Pregnancy Registry.

Follow-up is conducted to obtain pregnancy outcome information for all EIU reports. The Investigator will follow the pregnancy until completion (or until pregnancy termination) and notify the Sponsor of the outcome as a follow-up to the initial EIU Form. In the case of a live birth, the structural integrity of the neonate can be assessed at the time of birth. In the event of a termination, the reason(s) for termination should be specified, and, if clinically possible, the structural integrity of the terminated fetus should be assessed by gross visual inspection (unless pre-procedure test findings are conclusive for a congenital anomaly and the findings are reported).

If the outcome of the pregnancy meets the criteria for an SAE (i.e., ectopic pregnancy, spontaneous abortion, intrauterine fetal demise, neonatal death, or congenital anomaly [in a live born, a terminated fetus, an intrauterine fetal demise, or a neonatal death]), the Investigator should follow the procedures for reporting SAEs.

Additional information about pregnancy outcomes that are reported as SAEs include:

- Spontaneous abortion includes miscarriage and missed abortion;
- Neonatal deaths that occur within one month of birth should be reported, without regard to causality, as SAEs.
- Death of an infant older than one month should be reported as an SAE if the Investigator assesses the infant death as related or possibly related to exposure to investigational product.

Additional information regarding the exposure during pregnancy may be requested by the Investigator. Further follow-up of birth outcomes will be handled on a case-by-case basis (e.g., follow-up on preterm infants to identify developmental delays). In the case of paternal exposure, the investigator will provide the study subject with a Pregnant Partner Release of Information Form to deliver to his partner. The Investigator must document on the EIU Form that the subject was given this letter to provide to his partner.

# 8.4. Data Safety Monitoring Board (DSMB)

An independent Data Safety Monitoring Board (DSMB) will meet at specified times throughout the study to review the accumulation of data. The DSMB will consist of at least 3 members, including a statistician. No Investigator involved in the trial or anyone connected to the Sponsor or participating vendors such as a CRO may be a member of the DSMB. Based on the review of the study data, the DSMB may make recommendations regarding the conduct of the study. These may include, but are not limited to, amending safety monitoring procedures, modifying the protocol or consent, terminating the study, or continuing the study as designed. The discussions and decisions of the DSMB will be summarized in written minutes and provided to the Sponsor. When necessary, summary DSMB minutes may be distributed to participating sites for submission to Ethics Committees. A separate DSMB Charter will direct the activities of the Board.

The approximate timing of DSMB meetings are noted below:

- After a minimum of three (3) subjects from Cohort 1 have reached the Week 4 clinic visit and the results are available, the Sponsor then has the ability to request the DSMB to meet. The available cumulative data collected in all subjects from Cohort 1 up until that time will be evaluated by the DSMB. Based on review of the available data, the DSMB will make a recommendation on the enrollment of Cohort 2. The DSMB will not meet regularly during Cohort 1 unless there is a related AE that requires an independent DSMB review.
- Quarterly during the first year of Cohort 2, and thereafter every three (3) to six (6) months until the last visit of the last Cohort 2 subject has occurred.

Additional meetings of the DSMB may be scheduled based on data review needs or by request.

# 8.5. Study Stopping Rules

If any of the following safety events are noted to occur in the study, an ad-hoc meeting of the DSMB will be requested. The DSMB will review the data and will recommend stopping the study for any of the following:

- 1. Two or more subjects have pronounced immune responses to VC-02.
- 2. Two or more subjects experiencing a NCI-CTCAE Grade 3 (severe) treatment emergent adverse event (TEAE) in the same Medical Dictionary for Regulatory Activities (MedDRA) system organ class (SOC) and preferred term (PT) considered to be possibly or probably related to the investigational product. TEAE is defined as an AE that starts on or after the date of implant surgery.
- 3. After a minimum of eight weeks post-implantation, there are two or more subjects who each experience two or more Severe Hypoglycemic Events (SHE) over a 6-month period unrelated to anything other than VC-02. This assumes the SHE occurred despite reasonable adjustments in the exogenous insulin requirements and appropriate dietary adjustments.
- 4. Two or more subjects develop SAEs deemed related to the implantation of VC-02 itself; examples of such events are noted below:
  - a. Development of an off-target cell growth (i.e., teratoma) within the unit which is noted on ultrasound and confirmed by pathologist.
  - b. A related, severe, persistent, inflammatory response that does not resolve (e.g., severe site reactions, urticaria, erythematous rash, anaphylaxis, acute respiratory insufficiency, swelling).
- 5. Two or more subjects have an unexplained graft malfunction requiring explant.

In addition to these events, the DSMB can consider recommending a temporary delay or hold on enrollment in the trial for events considered by the Investigator to be related to VC-02. The DSMB can also recommend treatment continue for a shorter duration (i.e., less than the planned two years) or with a fewer number of implanted units. The DSMB can also recommend the Sponsor close the study at any time in response to any legitimate safety concerns. The Sponsor will communicate DSMB recommendations to each site in a timely fashion. Each site's Ethics Committee will make the ultimate decision to delay enrollment, modify treatment duration, or stop the study based on DSMB recommendations.

The Sponsor may also decide to terminate the study for other safety or lack of efficacy reasons. In the event the study is terminated, all subjects will have their VC-02 units explanted, and all subjects will be followed post-explant in a long-term follow-up study (VC02-201).

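### Stopping rule 2 names a causality level that is not on the trial's scale (probably) and leaves out the strongest one that is (definitely)

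*Protocol*

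**What the plan says.** Protocol 8.5 lists five events. If any occurs, an ad hoc DSMB meeting is to be requested and the DSMB is to recommend stopping. Rule 2 concerns two or more subjects with a Grade 3 treatment-emergent event in the same system organ class and preferred term, "considered to be possibly or probably related to the investigational product".

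Protocol 8.1.1 defines the causality scale. Its levels are Not Related (covering unrelated and unlikely), Possibly Related and Definitely Related. The top level requires a plausible time relationship "and which cannot be explained by concurrent disease or other drugs or chemicals". SAP 7.2.3 gives the same three levels.

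Other passages bear on how far the mismatch reaches:

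- Protocol 8.1 defines a severe event as "Medically significant but not immediately life threatening, hospitalization or prolonged hospitalization". It separates severity from seriousness with an example: "a headache may be severe (medically significant) but would not be classified as serious unless it met one of the criteria for SAEs".
- Protocol 8.2 makes an event serious if, among other criteria, it "Requires in-patient hospitalization or prolongation of existing hospitalization" or "Constitutes an Important Medical Event in the opinion of the Investigator and/or Sponsor".
- Protocol 8.1 adds that "any non-serious AE that is determined by the Sponsor to be serious will be reported by the Sponsor as a SAE".
- Rule 4 of Protocol 8.5 covers the case "Two or more subjects develop SAEs deemed related to the implantation of VC-02 itself".

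**The concern.** The rule and the scale do not share a vocabulary. Probably Related is not a defined rating, and Definitely Related is defined but not mentioned in the rule. Neither document maps one term to the other. Taken at its words, the rule responds to the weaker related rating and is silent on the stronger one, which is the reverse of what a safety trigger should do.

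At stake is whether the response is obligatory. For the five listed events the meeting and the stop recommendation are prescribed. The DSMB's wider powers in Protocol 8.5, to recommend a hold or closure, are only permissive. Someone also has to screen events against rule 2 before the DSMB is convened, so the wording matters before the DSMB has any chance to interpret it.

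**Working it through.** No sample size, power or event rate enters this point, and the plan gives no figure to reproduce. The check is a comparison of terms.

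**Step 1. Terms against the scale.**

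| Term | Defined in Protocol 8.1.1 and SAP 7.2.3? | Named in rule 2? |
|---|---|---|
| Not Related | yes | no (correctly) |
| Possibly Related | yes | yes |
| Probably Related | no | yes |
| Definitely Related | yes | no |

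The scale has 3 levels, of which 3 − 1 = 2 are related levels. Rule 2 names 2 terms, of which 1 is on the scale. It therefore reaches 1 of the 2 related levels.

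**Step 2. Literal effect for two subjects** with the same Grade 3 system organ class and preferred term:

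| Ratings of the two subjects | Rule 2 as written | With definitely in place of probably |
|---|---|---|
| Possibly, Possibly | met | met |
| Possibly, Definitely | not met | met |
| Definitely, Definitely | not met | met |

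With more than two subjects, the rule as written fails whenever no more than one of them is rated Possibly Related and the rest Definitely Related.

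**Step 3. Usage elsewhere.** Three places set an inclusion threshold by pairing possibly with definitely: Protocol 8.1.4 and SAP 7.2.4 (adverse events of special interest) and SAP 7.6.3 (implant tolerability). Rule 2 is the only place that pairs possibly with probably. The intended meaning can be inferred from this, but it is not stated.

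**Step 4. What the other rules already catch.** A Grade 3 event involving hospitalization, or judged an important medical event, is serious under Protocol 8.2. The Sponsor can also upgrade an event under 8.1. If related to VC-02, such events come under rule 4. Rules 1, 3 and 5 cover pronounced immune responses, repeated severe hypoglycemia and unexplained graft malfunction. What is left is non-serious Grade 3 events outside those rules. The headache example in 8.1 shows that the protocol recognises severe events that are not serious.

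**The case against.** The strongest reply is that possibly works as a floor. Protocol 8.1.5 asks for late SAEs assessed as possibly related to be reported, and nobody would take that to exempt definitely related ones. Read that way, rule 2 has no gap, and a DSMB would probably read it so. However, the sentence in 8.1.5 states outright that it sets a minimum. Rule 2 has no such phrase and instead lists two levels.

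Second, the residual set is narrow. Definitely Related is a demanding rating in subjects who are all prescribed immunosuppression, although local implant-site events could meet it. This stands, and it is why the effect is modest.

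Third, there are other safeguards: scheduled DSMB meetings and extra ones on request (8.4), Sponsor termination (8.5), and subject-level withdrawal criteria (13.6). These soften the consequence. They are discretionary, periodic or confined to one subject, so they do not replace a prescribed trigger.

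Fourth, the DSMB charter and the case report form are not among the documents. Protocol 10.3.1 says the charter holds the definitions used to assess specific safety events, so it may resolve the matter. That limits any claim about operation, but the mismatch in the protocol text remains.

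Finally, 8.1.1 classifies events of unknown causality as related for reporting purposes, and the proposed wording does not mention them. That is a reporting convention, not a further level on the scale. It neither supplies a meaning for probably nor counts against the change.

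**Conclusion.** The concern holds. In the current text, a prescribed stopping rule uses a level that the scale does not contain and omits the strongest level that it does. On a literal reading, rule 2 misses the same non-serious Grade 3 event in two or more subjects when no more than one is rated Possibly Related, the rest are rated Definitely Related, and rules 1, 3 and 5 do not apply. No frequency can be attached to this.

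The practical effect is modest. The wording mismatch itself is certain. An operational gap exists only if the rule is applied literally and the charter does not define the terms otherwise. The correction should be made, because a first-in-human stopping rule should not depend on a charitable reading.

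**What to change.** In Protocol 8.5, rule 2, change probably to definitely, so that the threshold reads *possibly or definitely related to the investigational product*. This covers both related levels on the scale and matches Protocol 8.1.4, SAP 7.2.4 and SAP 7.6.3. Put the same wording in the DSMB charter.

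Do not shorten the phrase to *related*. SAP 7.2.3 defines a combined related category that also takes in events rated Unlikely Related, and borrowing that term would make the threshold unclear again.

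The cost is one word at the next protocol amendment and a matching line in the charter. Both levels are already on the scale in Protocol 8.1.1, so data collection and analysis do not change.
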